1 INVESTIGATIONAL PLAN

1.1 Purpose

The purpose of this randomized controlled trial is to assess and compare radiographic and clinical outcomes in patients who are to undergo combined interbody/posterolateral lumbar fusion procedures, supplemented with pedicle screw instrumentation, using one of the following interbody cages; the Nexxt Spine Nexxt Matrixx[™] 3D-printed titanium cage or the Honour[™] poly-ether-ether-ketone cage.

2 INTRODUCTION

2.1 Background

In 2012, over 727,000 spinal fusion and non-fusion procedures were performed in the US (Millennium Research Group (MRG), 2013). This included treatment for various conditions such as DDD, spinal stenosis, spondylosis, spondylolisthesis, spinal deformities, tumors, and traumatic spinal injuries. Over time, intervertebral discs wear down and lose water and then disc height. The degeneration of these discs can impact the spine in several ways, including spinal canal stenosis, spondylolisthesis, and osteophyte and bony growth formation. These changes can impinge on the spinal cord and nerve roots, causing chronic pain. Consequently, as the older population in the US expands, demand for treatments that address back and extremity pain will rise accordingly. The correlation between age and the incidence of DDD has been well-documented; for example, one study concluded that there was a direct relationship between age and the macroscopic grade of degeneration caused by DDD (Quint and Wilke, 2008). Increasing rates of obesity in the US will also likely contribute to growth in spinal fusion and non-fusion volumes because obesity represents a risk factor for DDD (Hangai M, et al., 2008).

The premise behind fusion surgery for lower back pain (LBP) and leg pain is that a degenerated and mobile lumbar segment acts as a pain generator. Consequently, if motion is prohibited through a fusion, it is expected that the patient will experience improvement in both pain and disability, which will increase their ability to function. Currently, there is no way to be certain which structure or structures actually are causing the pain, but the main interest has been focused on the facet joints, discs, or a combination of both (Fritzell P et al., 2002).

Lumbar spine fusion rates can vary according to the surgical technique. Although many studies on spinal fusion have been conducted and reported, the heterogeneity of the study designs and data handling make it difficult to identify which approach yields the highest fusion rate. Traditional posterolateral inter transverse process fusion (PLF) still remains a good procedure with acceptable fusion rates for most degenerative conditions. For solid fusion, PLF can be combined with interbody fusion (IF) to circumferentially stabilize the relevant segment, even though it is unclear whether this improves the rate of fusion (Lee et al, 2011).

A bone graft or bone graft substitute is required to produce the fusion and can be implanted on its own, in the posterolateral gutters, or contained with an interbody device using either a posterior or anterior approach. Spinal fusion procedures are the largest source of bone graft product use. The current gold standard is autograft bone, wherein tissue is harvested from the patient, usually from the iliac crest or locally, and is then placed over the fusion surfaces. Autograft is the gold standard because it possesses all of the characteristics necessary for new bone growth namely, osteoconductivity, osteogenicity, and osteoinductivity. Osteoconductivity refers to the situation in which the graft supports the attachment of new osteoblasts and osteoprogenitor cells, providing an interconnected structure through which new cells can migrate and new vessels can form. Osteogenicity refers to the situation when the osteoblasts that are at the site of new bone formation are able to produce minerals to calcify the collagen matrix that forms the substrate for new bone. Osteoinductivity refers to the ability of a graft to induce nondifferentiated stem cells or osteoprogenitor cells to differentiate into osteoblasts (Laurencin C. et al., 2006).

The mechanical and structural properties of an interbody device are used to support osteogenesis across the interbody space and contribute to the success of a spinal fusion procedure. One of the most popular synthetic implant materials is poly-ether-ether-ketone (PEEK). PEEK is used as a spacer between vertebrae while providing surfaces allowing for bone formation. While macroscale properties such as implant shape contribute to the growth of a fusion mass, microscale properties such as implant topography likely play a much larger role through facilitating osteoblastic differentiation, osteoid synthesis, and mineralization.

Recent studies have shown that PEEK does not integrate well with the surrounding bone and instead may form a fibrous connective interface (Kurtz and Devine, 2007; Anjarwalla et al., 2006). Recently, the relative failure of osseo-integration observed with PEEK implants has been demonstrated to be associated with the reduced ability of cells on the implant surface to generate an environment rich in angiogenic factors. In contrast, implants fabricated from titanium result in good bone-to-implant contact and are osseo-integrated into the surrounding bone. Osteoblasts

on rough titanium substrates have been shown to produce angiogenic factors including significantly higher VEGF-A and FGF-2 levels on smooth and rough titanium alloys than on PEEK, an effect significantly more robust on rough titanium alloy (Olivares-Navarrete et al., 2013).

2.2 Device Description

Subjects enrolled in this study will have either the Nexxt Spine Nexxt MatrixxTM 3Dprinted titanium cage or the HonourTM PEEK cage implanted at each level of 1 or 2-level lumbar arthrodesis procedures. All constructs will be supplemented with a pedicle screw system (Depuy Synthes Expedium) cleared for lumbar spinal fusion.

Nexxt Matrixx[™] interbody fusion cages are manufactured with detailed specifications utilizing modern 3-D printing technology to replicate the cellular structure of cancellous bone. 3-D printing technology allows for the creation of a complex lattice geometry that cannot be created by traditional orthopedic manufacturing processes. First, a uniform 3-D architecture with a consistent 70% porosity provides an optimal biomechanical and biological environment for promotion of osseous tissue regeneration throughout implant walls. Second, an interconnected array of 300-700µm pores creates ideal an environment for natural influx of proteins, hormones, growth factors and mesenchymal stem cells to promote osteoinduction.

In a review article by Karageorgiou and colleagues (2005), a noted minimum pore size of 100 µm was reported to be more conducive to bone ingrowth than pore sizes less than 75 µm. However, the authors recommended pore sizes greater than 300 µm as other studies have shown a better osteogenic response. In a transcortical rabbit study, titanium alloy (Ti6Al4V) implants with 100, 200, and 300 µm pores were compared; the larger pore sizes resulted in a higher percentage of bone within the pores and a higher percentage of that bone to be lamellar (Götz HE et al., 2004). Another study used a 3D-printed Ti6Al4V scaffold implanted over the transverse process of goats to study the effects of pore size and porosity on osseointegration (Li JP et al., 2007). Five groups of implants having a pore size and porosity ranging from 160µm/39% to 680µm/68% were evaluated. While the small sample size prevented an evaluation of statistical significance, data trends led to the conclusion that the larger pores and porosity allow for greater amounts of newly formed bone. Taken together, these studies support the varied porosity selection of 300-700µm pore size of the Nexxt Matrixx[™] System implants.

An additional parameter evaluated is the surface finish (Götz HE et al., 2004). One set of the 200µm implants were surface-blasted using an aluminum oxide such that a roughness average (Ra) of 7.25µm resulted. The effect of this roughness was an increase in the bone-implant contact overall on the surface and within the pores. However, a later study (Nakada H. et al, 2007) compared osseointegration when alumina and a multiphase calcium phosphate (MCD) were used as the blast media. Blasted Ti6Al4V cylinders were implanted into rabbit tibiae and were then evaluated two and four weeks after implantation. The histologic results showed the MCD to illicit a greater volume of new bone formation. The MCD used in this study is the same as the calcium phosphate blast media used in the manufacture of the Nexxt Matrixx[™] System implants.

The Nexxt Matrixx[™] System implants have a roughened surface with a Ra measurement ranging from 5.0 to 11.8 that is attained via a calcium phosphate surface-blasting process. As stated above, this surface was selected specifically due to its capacity for osseointegration.

3 TRIAL DESIGN

3.1 Design

The randomized controlled trial will prospectively evaluate the safety and efficacy of the Nexxt Matrixx[™] System titanium implant supplemented with a pedicle screw system as compared to a representative PEEK cage currently used in routine fashion for lumbar interbody fusion procedures. This study will capture clinical and radiographic outcomes on patients up to 2 years post operatively. Both cages will be used in conjunction with milled local autograft bone generated as part of the spinal fusion procedure (no iliac crest autograft will be utilized).

This single centered study will enroll up to 70 subjects (n = 35 per group), with subjects followed for a minimum of 12 months post-surgery. All subjects enrolled in the study will be recruited from a pool of subjects eligible for combined interbody/posterolateral lumbar fusion surgery. The inclusion/exclusion criteria are listed below.

3.2 Inclusion Criteria

Subjects will be considered for inclusion in this trial if they satisfy the following criteria.

- Subject is scheduled to undergo combined interbody and posterolateral spinal fusion surgery using either the Nexxt Matrixx[™] 3D-printed titanium cage or Honour[™] PEEK cage in conjunction with local autograft bone, and supplementation with a pedicle screw system.
- 2. Subject must be over the age of 18 years old.
- 3. Subject has been unresponsive to conservative care for a minimum of 6 months.
- 4. The subject must in the investigator's opinion, be psychosocially, mentally, and physically able to fully comply with this protocol including the required follow-up visits, the filling out of required forms, and have the ability to understand and give written informed consent.

3.3 Exclusion Criteria

Subjects will be excluded from this trial if they satisfy any of the following criteria:

- 1. Subjects with previous lumbar arthrodesis surgery.
- 2. Subjects requiring additional bone grafting materials other than local autograft bone.
- 3. Subject has inadequate tissue coverage over the operative site.
- 4. Subject has an open wound local to the operative area, or rapid joint disease, bone absorption, or osteoporosis.
- 5. Subject has a condition requiring medications that may interfere with bone or soft tissue healing (i.e., oral or parenteral glucocorticoids, immunosuppressives, methotrexate, etc.).
- 6. Subject has an active local or systemic infection.
- 7. Subject has a metal sensitivity/foreign body sensitivity.
- 8. Subject is morbidly obese, defined as a body mass index (BMI) greater than 40.
- 9. Subject has any medical condition or extenuating circumstance that, in the opinion of the investigator, would preclude participation in the study.
- 10. Subject is currently involved in another investigational drug or device study that could confound study data.
- 11. Subject has a history (present or past) of substance abuse (recreational drugs, prescription drugs or alcohol) that in the investigator's opinion may interfere with protocol assessments and/or with the subject's ability to complete the protocol required follow-up.
- 12. Subjects who are pregnant or plan to become pregnant in the next 12 months or who are lactating.

- 13. Subject is involved in or planning to engage in litigation or receiving Worker's Compensation related to neck or back pain.
- 14. Subject is a prisoner.

4 STUDY PROCEDURE

4.1 Screening Assessments

4.1.1 Informed Consent

Subjects will be provided with an informed consent and will be given ample opportunity to review the consent and ask questions. The signed informed consent will be obtained before any study specific procedures, that are not part of the investigator's standard of care begin. A copy of the informed consent will be given to the subject. All subjects who meet all of the entry criteria will be considered for inclusion in this trial. Any subject meeting any of the exclusion criteria will be excluded from the trial.

All subjects who have agreed to participate in this study, have signed the informed consent and who meet the inclusion/exclusion criteria will be considered enrolled and assigned a subject ID number. Once a Subject ID number has been issued, it cannot be reassigned or used for another subject.

4.1.2 Medical History and Demographic Data

Within 60 days prior to the surgery date, the following information will be collected:

- Demographic data
- Medical history, including a complete history of spinal disorder(s) (nonoperative or operative treatments performed)
- Physical examination (including height, weight)
- X-Rays
- Current pain medications and other drug therapies.
- Neurological status All subjects' neurological status will be assessed and recorded as intact or not intact, based upon the investigator's motor, sensory and reflex evaluations.

4.1.3 Pregnancy Screening

A pregnancy test will be performed and negative results shall be kept on file for all female subjects unless infertile or post-menopausal to ensure subjects are not enrolled into the study who are pregnant.

4.1.4 Clinical Assessments

Subject study data will be collected preoperatively, intra-operatively and postoperatively at 3, 6, 12, and when available 24 months. The following data will be recorded on the Case Report Forms (CRFs) and in addition, electronic data entry will be employed via an Internet connection when possible using the Research Electronic Data Capture (REDCap) program.

Oswestry Disability Index version 2.1a (ODI v2.1a): Pre-operatively the subject will complete the Oswestry Disability Index for a baseline low back pain and function assessment. The questionnaire is a combined pain and function index which will be used to assess the subject's back pain and how that pain affects the subject's ability to manage in everyday life. The questionnaire is divided into ten sections designed to assess limitations of various activities of daily living. Each section contains six statements and each statement describes a greater degree of difficulty in that activity than the preceding statement. The subject marks the one statement in each section, which describes his/her limitations most accurately. Each section is scored on a 0-5 scale, 5 representing the greatest disability. The scores for all sections are added together, giving a possible score of 50. The total is doubled and expressed as a percentage. If a subject marks two statements, the highest scoring statement is recorded as a true indication of his disability. If a section is not completed because it is inapplicable, the final score is adjusted to obtain a percentage.

Back and Radicular Leg Pain: Preoperatively all subjects will assess their back and/or radicular leg pain in one or both legs using a visual analog scale (VAS) from 0 - 10 with 10 being considered most painful.

4.2 Randomization

All subjects will be randomized in the trial to receive either the Nexxt Spine Nexxt MatrixxTM 3D-printed titanium cage or the HonourTM PEEK cage supplemented with a pedicle screw system and milled local autograft bone. Subject randomization will be stratified according to smoking status. Subjects will be blinded to their group status for the duration of the study assessments and procedures (12 months post-operatively).

4.3 **Perioperative and Postoperative Management**

Surgeons will perform combined interbody and posterolateral lumbar fusion utilizing either Nexxt MatrixxTM or PEEK cages supplemented with a pedicle screw system cleared for fusion and milled local autograft bone (per customary protocol).

Data will be collected during and immediately after the surgery according to the parameters described by the Nexxt Matrixx[™] IF/PLF CRFs. This includes: diagnosis, duration of surgery, blood loss, OR time, length of hospital stay, instrumentation used, type of procedure, and surgical level(s). In addition, all intra-operative complications (e.g. excessive blood loss, hematoma, vascular injury, etc.) will be reported and recorded as a complication on the CRF.

Intra-operative (after hardware installation is completed) or immediate postoperative x-rays will be obtained. Postoperative care will follow the standard of care at each institution for subjects who undergo fusion procedures.

Postoperative care is extremely important. The subject should be warned that noncompliance with postoperative instructions could lead to breakage of the pedicle screw system and/or possible migration requiring revision surgery to remove the pedicle screw system.

Screening/	Procedure	3 months	6 months	12 months	24 months
Enrollment		(± 7 days)	(± 14 days)	(± 30 days)	(± 60 days)
procedure)					
Х					
Х					
Х					
Х	Х	Х	Х	Х	X**
	Х				
Х		Х	Х	Х	X**
X		Х	X	Х	X**
X		Х	X	Х	X**
			X*		
Х	Х	Х	Х	Х	X**
	Enrollment (-60 days of procedure) X X X X X X X X X X X X	Enrollment (-60 days of procedure) X X X X X X X X X X X X X X X	Enrollment (-60 days of procedure)(± 7 days)X	Enrollment (-60 days of procedure)(± 7 days)(± 14 days)XXX	Enrollment (-60 days of procedure) $(\pm 7 days)$ $(\pm 14 days)$ $(\pm 30 days)$ X </td

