4.7 Success Criteria

4.7.1 **Primary Measure of Effectiveness**

A subject will be considered a success if fusion is a Grade BSF-3 at 6 months. The primary outcome measure of effectiveness will be determined by the fusion rate at 6 months post-operatively in subjects implanted with either titanium cage as compared to the PEEK cage.

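### Number of fused levels (1 or 2) is neither a stratification factor nor a listed screening item: a minor gap in balance, cheaply closed by recording planned levels before randomisation

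*Combined protocol and SAP*

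**What the plan says.** - **Scope.** Section 2.2 says cages are "implanted at each level of 1 or 2-level lumbar arthrodesis procedures". This is where the one-or-two-level limit is stated.
- **Entry.** Inclusion criterion 1 in Section 3.2 begins "Subject is scheduled to undergo combined interbody and posterolateral spinal fusion surgery". None of the 4 inclusion or 14 exclusion criteria mentions the number of levels.
- **Screening data.** Section 4.1.2 lists demographics, history ("Medical history, including a complete history of spinal disorder(s"), physical examination, X-rays, medication and neurological status. Planned levels are not listed.
- **Allocation.** Section 4.2 states: "Subject randomization will be stratified according to smoking status". It names no other factor and gives no block size or timing. Section 3.1 sets the size ("enroll up to 70 subjects (n = 35 per group").
- **Operative data.** Section 4.3 lists, among items gathered at and just after surgery, "instrumentation used, type of procedure, and surgical level(s".
- **Blinding.** Section 4.2 covers subjects: "Subjects will be blinded to their group status for the duration of the study assessments". Nothing is said about the surgeon.
- **Endpoint.** Section 4.7.1: "A subject will be considered a success if fusion is a Grade BSF-3 at 6 months". No rule is given for a subject with two levels.
- **Analysis.** Section 6 names no model, covariate or adjustment.

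**The concern.** Success is counted once per subject, but some subjects have one fusion site and others two. If a two-level subject counts as a success only when both sites fuse, that subject has a lower chance of success whichever cage is used. A trial with more two-level subjects in one arm would then show a difference that partly reflects case mix.

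Nothing in the plan balances the arms on levels, and no adjustment is planned. The sections that can be read also do not provide a pre-randomisation record of planned levels on which an adjustment could rest. At stake is how easily a modest difference, in either direction, could be attributed to case mix.

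**Working it through.** The plan gives no figure on case mix to reproduce, and no inputs from which its sample size could be rebuilt. The only input taken from it is 35 per arm. The two-level share, per-level fusion rate, within-subject correlation, smoking prevalence and block size are assumptions, shown as ranges where they matter.

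**Step 1: chance imbalance in the two-level share, levels ignored at allocation.** Let K of the 70 subjects be two-level, with share s = K/70. The number falling in one arm is hypergeometric. The between-arm difference in share has SD = 2 × √(s(1 − s)/69).

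| s | K | SD of difference | Smallest split with gap ≥ 20 points | P(gap ≥ 20 points) |
|---|---|---|---|---|
| 0.30 | 21 | 0.110 | 14 v 7 | 0.117 |
| 0.40 | 28 | 0.118 | 18 v 10 | 0.087 |
| 0.50 | 35 | 0.120 | 21 v 14 | 0.151 |

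Simulating permuted blocks of 4 within smoking strata (20% smokers assumed) gives an SD of 0.110-0.119 and P(gap ≥ 20 points) of 0.075-0.091. Stratifying by smoking does almost nothing to balance levels.

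**Step 2: effect of two levels on success, if both must fuse.** With per-level fusion p and within-subject correlation ρ, two-level success is p² + ρp(1 − p). The gap from one-level success is therefore (1 − ρ)p(1 − p).

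| p | Gap, ρ = 0 | Gap, ρ = 0.5 |
|---|---|---|
| 0.6 | 0.240 | 0.120 |
| 0.7 | 0.210 | 0.105 |
| 0.8 | 0.160 | 0.080 |
| 0.9 | 0.090 | 0.045 |

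**Step 3: shift in the cage difference.** Shift = gap × imbalance. At a 20-point imbalance this runs from 0.045 × 0.20 = 0.009 to 0.240 × 0.20 = 0.048, or about 1-5 points.

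**Step 4: compare with sampling error.** Overall success is π = p − s × gap, and the standard error of the arm difference is √(2π(1 − π)/35).
- p = 0.6, ρ = 0, s = 0.5: π = 0.48, SE = 0.119, and the shift of 0.048 is 0.4 SE.
- p = 0.9, ρ = 0.5, s = 0.3: π = 0.8865, SE = 0.076, and the shift of 0.009 is 0.1 SE.

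**Step 5: type I error.** These are simulations with a pooled z-test, two-sided 0.05, p = 0.7-0.9, ρ = 0 and no cage effect.
- Same 40% chance of a two-level procedure in both arms: rejection rate 4.8-5.4%, close to nominal.
- Two-level chance made to depend on arm (30% v 50%, purely illustrative): false difference of about 2-4 points, rejection rate 5.9-6.5%.

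**Step 6: effect of the fix.** With blocks of 4 within smoking × levels (four strata, 20% smokers), the SD of the imbalance falls to 0.026-0.028. None of the 10,000 simulated trials per setting reached a 10-point gap.

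**The case against.** The strongest reply has four parts.

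1. **Chance imbalance is not bias.** Randomisation already allows for it, and Step 5 agrees. A shift of 0.1-0.4 SE that needs an imbalance seen in at most 15% of trials is small. This stands, and it is why the point is minor.

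2. **The size depends on a missing rule.** The gap in Step 2 requires that both levels fuse. If one index level were graded, arithmetic alone gives no gap. If one fused level sufficed, the gap would reverse (at p = 0.7 with independent levels, 1 − 0.3² = 0.91 against 0.70). This stands too. A reader might infer that the number of levels is a strong driver of fusion, but the documents do not say so.

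3. **Choice of levels after allocation is not shown.** A reader might infer that an unblinded surgeon chooses the levels once the cage is known, or that levels are captured only in operative data. Neither is supported. Criterion 1 has surgery already scheduled at entry. The Section 4.3 list also includes diagnosis, which exists before surgery, so the list shows when an item is recorded and not when it is decided. The timing of randomisation is not stated. The case report forms and the row labels of the schedule table are not visible, so planned levels may be recorded at screening. If cage type does not influence levels, adjusting for operated levels would also be harmless.

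4. **The scope is stated.** A reader might infer that a three-level case is eligible. Section 2.2 limits enrolled subjects to one or two levels. The limit is missing only from the entry criteria.

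What remains is that smoking is the sole named factor, the visible screening list omits planned levels, and no adjustment is planned.

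**Conclusion.** The point holds as a minor design improvement. The number of levels is left to chance at allocation, and the readable text does not secure a baseline record of it. At 35 per arm with a 30-50% two-level share, a gap of 20 points or more is expected in about 9-15% of trials (about 7.5-9% with blocks of 4 within smoking strata). If both levels must fuse, with p = 0.6-0.9 and ρ = 0-0.5, two-level success is about 4.5-24 points lower, and such a gap shifts the cage difference by about 1-5 points.

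The consequence is some loss of precision and credibility. It would be wrong to conclude that the design inflates type I error or is biased. That would require levels to be chosen differently by arm, which is possible under the text but not shown by it.

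**What to change.** - **Section 3.2:** state the existing one-or-two-level scope from Section 2.2 as an inclusion criterion.
- **Section 4.1.2 and screening form:** record the planned number of levels before randomisation, or confirm that this is already done.
- **Section 4.2:** stratify by smoking status and planned levels (1 v 2), giving four strata, with small blocks.
- **Section 6:** base any level-adjusted or subgroup analysis on planned levels, not operated levels.
- **If enrolment has begun:** leave the list as it is and adjust the primary comparison for planned levels, which should recover most of the gain.

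The cost is one screening field, one line in the criteria and a regenerated list. The downside is that some strata, such as two-level smokers, will be small. The rule for scoring a two-level subject is a separate matter that this change does not settle.
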